#### 6.2.2 Clinical outcome assessment

Clinical status at 3-6 months and 12-18 months follow-up will be recorded as a secondary outcome. This will include a NIH Stroke Scale and modified Rankin Scale as administered by a member of the research team at the time of the follow-up angiograms. Members of the treatment team may not administer these questionnaires. This data should be collected by a qualified, independent physician. If a qualified, independent practitioner is not available, a clinical research coordinator or nurse may administer the questionnaire, as long as they are not a member of the treatment team. The modified Rankin Scale and NIH Stroke Scale will be entered into the web-based data entry form.

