## **4.2 Exclusion Criteria**

1. Patient has more than one aneurysm requiring treatment in the current treatment session, and only one of those to-be treated aneurysms fits the FEAT inclusion criteria (i.e., - if either (1) a patient has multiple aneurysms, but only one will be treated at enrollment; or (2) if two or more aneurysms are treated during the current treatment session and BOTH are able to be enrolled, then they remain eligible for the trial. Non-treated additional aneurysms may be treated at a later date with any coil type that the operator chooses).
2. Target aneurysm has had previous coil treatment or has been surgically clipped.
3. Hunt and Hess score is 4 or 5 after subarachnoid hemorrhage.
4. Inability to obtain informed consent.
5. Medical or surgical co-morbidity such that the patient's life expectancy is less than 2 years.

Death or procedural/disease-related morbidity may result in some subjects not having follow-up angiography. For the primary outcome of angiographic recurrence, the analysis will be conducted 2 ways: (1) among only those patients with angiographic assessment at 12-18 months, and (2) among patients with angiographic assessment, plus those with death or procedural/disease-related morbidity that precluded angiography, with such patients counted as incident events. Similarly, for the secondary outcome of treatment-related morbidity and mortality, patients without angiographic evaluation due to death or procedural/disease-related morbidity will be counted as incident events in the analysis.

Use of coil-assist devices (stent, balloon, etc.) will be allowed. Intention to use such a device will be recorded pre-procedure, along with dome to neck ratio and rupture status.

Additional critical components of the study design include the large number of patients required to demonstrate a statistically significant difference, and the subsequent significant length of time required to allow enrollment. Therefore, we propose a three phase study design to address the following concerns:

- 1) A 6-year time window renders any conclusions irrelevant due to progress in technology. Typically the conclusions of long-term studies in the endovascular space are called into question because they do not include technology that is considered modern by the time the study is completed. Stryker has multiple coil iterations planned over the next 5 years. To not involve these new technologies would make the study non-viable to

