#### 5.1.3 Follow-up

1. The following assessments will be performed at each standard care follow-up visit (3-6 months and 12-18 months post-coiling): (1) clinical outcome; (2) follow-up angiography/MRA; (3) modified Rankin Score; (4) NIH Stroke Scale.

2. The assessment window allowed for each follow-up visit is as follows: (1) 3-6 month follow-up allowable window is 3-7 months post-coiling; (2) 12-18 month follow-up allowable window is 10-20 months post-coiling.

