### ***5.2 Intention to Treat***

From the moment of randomization, the patient will be included in the trial irrespective of whether they receive the assigned treatment regimen. Similarly, all enrolled patients will receive clinical follow-up and will be included in the final analysis.

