### **6.6.3 *Modified Rankin Scale***

The number and percentage of patients in each mRS score category will be reported at the 3 to 6 month and the 12 to 18 month visits by group. For each visit, a Cochran-Mantel-Haenszel “shift” analysis (also known as van Elteren's test, Savitz 2007) will be used to evaluate differences in the mRS distribution between groups. The distribution of mRS

scores is expected to differ by aneurysm status. Analyses will be repeated separately by randomization strata for aneurysm status (recently ruptured vs. not recently ruptured).

Patients with missing mRS data at the 3 to 6 and/or 12 to 18 month visit will have their data imputed via multiple imputation assuming that the data are missing at random. The imputation model will be stratified by randomization assignment and aneurysm status and include age, sex, randomization strata for wide neck status, aneurysm size, and baseline mRS. Since this model includes a mixture of variables types (i.e. continuous, binary and ordinal), a fully conditional specification method will be used (Berglund 2014). Thirty datasets will be imputed and Rubin's methods will be used to combine them and estimate treatment effect (Rubin 1986).

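### The follow-up mRS is timed to the imaging visit, so disabled survivors who miss imaging may go unscored and then be imputed as missing at random

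*Combined protocol and SAP*

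**What the plan says.** Protocol 6.2.2 places the follow-up mRS and NIHSS at the imaging occasion: "This will include a NIH Stroke Scale and modified Rankin Scale as administered by a member of the research team at the time of the" imaging at that visit. Protocol 8.2 makes the 3-6 month and 12-18 month clinical status due within 72 hours of the follow-up image.

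Protocol 4.2 foresees missed imaging for clinical reasons: "Death or procedural/disease-related morbidity may result in some subjects not having follow-up angiography". Protocol 5.2, on the other hand, sets no imaging condition: "all enrolled patients will receive clinical follow-up and will be included in the final analysis".

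SAP 6.6.3 deals with absent scores as follows: "Patients with missing mRS data at the 3 to 6 and/or 12 to 18 month visit will have their data imputed via multiple imputation", under a missing-at-random assumption. The imputation is stratified by arm and aneurysm status and uses age, sex, wide-neck stratum, aneurysm size and baseline mRS. All of these are known before the procedure. No sensitivity analysis to that assumption is planned for mRS.

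SAP 6.8 names the 3-6 month mRS among the most important secondary endpoints and tests it in H3, and by aneurysm status in H4 and H5.

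**The concern.** The mRS needs no image, yet the protocol's operational instruction takes it when the image is taken. A survivor too disabled to travel for imaging then has no prescribed occasion for scoring and no data-entry deadline, while a well patient who returns is scored. Missingness would then depend on the value that is missing, which is the situation a missing-at-random model does not cover. The covariates in SAP 6.6.3 can say little about disability that arises during or after the procedure. Discharge mRS and NIHSS are collected (Protocol 6.1) but are not in the model.

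At stake are the reported level of disability in both arms and the between-arm comparison in H3 to H5. Few other planned analyses would pick up late disability, because the SAP's neurologic morbidity endpoint is fixed at 24 hours (SAP 5.2.1).

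**Working it through.** **Is there a figure to reproduce?** No. Neither document gives a rate of missing mRS or an expected mRS distribution. Every input below is an assumption, used only to show direction and scale.

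**Formula.** Let p be the true share of survivors with mRS 3-5 in an arm, d the proportion of those with no score, and n the proportion of other survivors with no score. If imputation is within arm and the covariates carry little information on disability, the imputed estimate tends to the share among scored patients:

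estimate = p(1 − d) / [p(1 − d) + (1 − p)(1 − n)]

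**Equal missingness.** Take p = 0.12 (smaller coils) and 0.15 (larger coils), with d = 0.5 and n = 0.1 in both arms.

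- Smaller: 0.12 × 0.5 / (0.12 × 0.5 + 0.88 × 0.9) = 0.060 / 0.852 = 7.0%
- Larger: 0.15 × 0.5 / (0.15 × 0.5 + 0.85 × 0.9) = 0.075 / 0.840 = 8.9%

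With d = 0.3 the estimates are 0.084 / 0.876 = 9.6% and 0.105 / 0.870 = 12.1%.

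**Effect on the comparison.** In each arm the odds of disability are multiplied by (1 − d)/(1 − n). If that factor is the same in both arms, it cancels from the odds ratio. If it differs, it does not.

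| Missing among disabled (smaller / larger) | Estimates (smaller / larger) | Difference, points | Odds ratio |
|---|---|---|---|
| none lost (truth) | 12.0% / 15.0% | 3.0 | 1.29 |
| 50% / 50% | 7.0% / 8.9% | 1.9 | 1.29 |
| 30% / 30% | 9.6% / 12.1% | 2.5 | 1.29 |
| 50% / 30% | 7.0% / 12.1% | 5.0 | 1.29 × 0.7/0.5 = 1.81 |
| 30% / 50% | 9.6% / 8.9% | −0.7 | 1.29 × 0.5/0.7 = 0.92 |

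The level is understated in every row with loss. The difference shrinks, grows or changes sign depending on how the loss falls between arms.

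**Other assumed inputs.** With 5% missing among patients with a good outcome and a true poor-outcome share of 15%, the estimate is 12.9%, 10.0% or 6.9% when 20%, 40% or 60% of poor outcomes lack a score.

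**Could better covariates repair it?** A large-sample simulation took a true share of 15%, 40% of poor outcomes and 5% of others missing, and assumed correlations with outcome of 0.3 for baseline status and 0.7 for discharge status. Imputation from baseline status alone gave 10.2%; adding discharge status gave 11.2%. Under these assumptions a richer model recovers only part of the loss.

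**The case against.** The strongest reply is that 6.2.2 says when the scores are taken, not that they are skipped without imaging. Protocol 5.2 requires clinical follow-up for all. Protocol 5.1.3 lists clinical outcome, imaging, mRS and NIHSS as separate items. The schedule in Protocol 6.1 has mRS at unscheduled visits, with imaging there only if indicated. Nothing forbids telephone scoring, and MRA is accepted in place of DSA. This stands to the extent that loss of scores is a risk from following 6.2.2 literally, not something the protocol orders. It does not remove the risk: 5.2 gives no mechanism, the items in 5.1.3 belong to one visit, MRA still requires attendance, and the only mention of telephone contact (Protocol 8.3) concerns data monitoring.

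Four stronger readings are tempting and are not supported:

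- *There is no way to score a patient without imaging.* The unscheduled-visit column in Protocol 6.1 contradicts this.
- *The same imputation problem affects NIHSS.* The only NIHSS endpoint in the SAP, and the only one imputed, is at 24 hours (SAP 5.2.1, 6.6.1).
- *Deaths are affected.* The scale in SAP 5.2.2 codes death as 6, so the issue is disabled survivors.
- *Any harm from larger coils is diluted.* The table shows an unchanged odds ratio under equal missingness and movement in either direction otherwise. SAP 6.6.3 plans a shift test on the whole mRS distribution, for which no effect was calculated here.

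Harm also has other routes to detection. Persistent disability is a serious adverse event (Protocol 7.2.1), reported whatever its cause and compared between arms (SAP 6.7.2). For treatment-related morbidity and mortality, Protocol 4.2 says that "patients without angiographic evaluation due to death or procedural/disease-related morbidity will be counted as incident events in the analysis", although the SAP's 24-hour definition does not carry that rule forward. These routes lower the stakes but do not replace the mRS. H3 to H5 are also formally tested only if H1 and H2 are both significant. The mRS results will be reported in any case.

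**Conclusion.** The concern holds in limited form. Protocol 6.2.2 and 8.2 tie the follow-up mRS to imaging, in tension with 5.2. Together with the loss of imaging anticipated in 4.2 and the missing-at-random imputation in SAP 6.6.3, this leaves a route by which the mRS of disabled survivors is selectively lost and filled in too favourably. The supported consequence is understated disability and a possibly distorted arm comparison.

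Neither the size nor the direction of that distortion can be derived from the documents. The fall from 12% and 15% to 7.0% and 8.9% rests on assumed disability rates, assumed missingness of 50% and 10%, and nearly uninformative covariates. The conclusion also depends on some sites reading 6.2.2 literally. It is confined to mRS in survivors.

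**What to change.** State in Protocol 6.2.2 that the mRS is obtained for every surviving patient within the windows already set in 5.1.3 (3-7 and 10-20 months), whether or not imaging is done. If the patient cannot attend, an assessor outside the treatment team takes the score by telephone or video from the patient or a caregiver, and the mode of assessment is recorded. Align Protocol 8.2 so that the deadline for clinical status runs from the clinical assessment rather than from the image.

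The cost is a few lines of protocol text, one case report form field and a short call for each non-attender. The downside is that a few scores will be remote and perhaps slightly less precise, which is preferable to having none. No endpoint, arm or aspect of care changes.

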## **5.5 Randomization**

1. A research team member authorized to randomize will then perform randomization via a web-based randomization process. The randomizer will communicate the result of the randomization to the neurointerventionalist who will coil the aneurysm. Alternatively, the neurointerventionalist can perform the randomization prior to performing the procedure.

2. An algorithm that stratifies the randomization will be used to ensure balance between the two treatment groups on those parameters known to significantly affect the ability to coil and pack densely. The stratification of these variables is as follows:

- Aneurysm status of recently ruptured (within 15 days) versus not recently ruptured;
- Current trial phase
- Dome to neck ratio:
  - Not wide neck – dome to neck ratio  $\geq 2$ , or neck width  $< 4\text{mm}$
  - Wide neck – dome to neck ratio  $< 2$ , or neck width  $\geq 4\text{mm}$

3. Both treatment arms are anticipated to have approximately equal proportions of acutely ruptured aneurysms. Aneurysm location will be recorded but will not be a basis of stratification due to lack of location as contributing to the recurrence or packing density achieved.

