## **8. Data Management and Entry**

### ***8.1 Data Collection***

1. Each site will be required to have a local coordinator who will be responsible for entering the study information into the web-based database and uploading the identifiable source documents/medical records associated with the study information. A web-based database housing the electronic case report forms (eCRFs) has been designed for the study, which will improve efficiency, lower cost of the study, and speed up publication of the results. Use of drop-down selection lists, radio buttons, checkboxes, and validation

checks will be incorporated to aid the speed, accuracy and consistency of data entry. The database will be backed up regularly.

2. Data collected will include: (1) enrollment and screening logs; (2) demographic data; (3) admission data (Hunt and Hess grade, Fisher grade, etc.) including the informed consent; (4) procedural data; (5) angiograms or MRA; (6) clinical course data; (7) 3-6 month angiogram or MRA; (8) 3-6 month clinical status; (9) 12-18 month angiogram or MRA; (10) 12-18 month clinical status; and (11) as needed additional follow-up data.

3. All data other than angiograms will be entered and/or uploaded into the web-based data entry forms. In addition, identifiable source documentation verifying all collected study data points will be securely uploaded into the web-based database.

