#### 3.1.2 Randomization and Masking

Patients will be randomly assigned in a 1:1 allocation to receive either larger or smaller coils. Patient randomization will be stratified by clinical site, aneurysm status (recently ruptured versus not), and dome to neck ratio (wide neck versus not). Randomization will be performed centrally through a web-based data collection system that automates the delivery of the randomization assignments.

Investigators will not be blinded to treatment assignment due to the nature of the treatment intervention. Investigators will, however, be blinded to all data from other clinical sites. Clinical outcome assessments will be completed by certified research staff that are not part of the treatment team. All angiograms will be analyzed by a blinded angiogram core laboratory personnel who will be blinded to clinical outcomes. Trial oversight will be provided by an independent Data and Safety Monitoring Board (DSMB).

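### The mRS and NIHSS assessors must be outside the treatment team but need not be unaware of the arm, which leaves two secondary endpoints in the testing hierarchy open to assessor bias among survivors.

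*Combined protocol and SAP*

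**What the plan says.** **Who scores.** Protocol 6.2.2 describes the clinical assessment at the 3-6 and 12-18 month visits: "This will include a NIH Stroke Scale and modified Rankin Scale as administered by a member of the research team". It states a preference, "This data should be collected by a qualified, independent physician", and then a fallback: "a clinical research coordinator or nurse may administer the questionnaire, as long as they are not a member of the treatment team". SAP 3.1.2 gives the general rule: "Clinical outcome assessments will be completed by certified research staff that are not part of the treatment team". The same section says of the investigators: "Investigators will not be blinded to treatment assignment due to the nature of the treatment intervention".

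**Who knows the arm.** Protocol 5.5 begins with "A research team member authorized to randomize will then perform randomization via a web-based randomization process" and continues with "The randomizer will communicate the result of the randomization to the neurointerventionalist who will coil the aneurysm". It also allows the neurointerventionalist to randomize instead. Protocol 8.1 requires each site to have a "local coordinator who will be responsible for entering the study information into the web-based database".

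**Where masking is stated.** Protocol 5.1.2 and 6.2.1 blind the imaging core lab, the latter explicitly to treatment arm. SAP 3.1.2 blinds the core lab to clinical outcomes. No section applies masking to the clinical assessors.

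**Where the scales are used.** SAP 6.8 puts 24-hour neurologic morbidity (an NIHSS worsening of at least 4 points, SAP 5.2.1) in the hierarchy as H2, and the 3-6 month mRS distribution as H3. H4 and H5 repeat H3 by rupture status.

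**The concern.** Being outside the treatment team is not the same as being unaware of allocation. A coordinator who randomized the patient, told the operator the result and later entered the procedure data meets every stated condition for scoring that patient's mRS.

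The mRS asks the rater to judge between adjacent grades of disability, and several NIHSS items also need judgement. A rater who knows the arm and expects one coil size to do better can shift scores without intending to. SAP 6.8 calls neurologic morbidity and 3-6 month mRS the most important secondary endpoints clinically, and claims type I error control for them. Gatekeeping controls chance error. It does not control a systematic scoring difference between arms. If the trial succeeds on occlusion, any accompanying claim of clinical benefit would rest on these scores.

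**Working it through.** **1. What the text permits**

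| Role | Stated condition | Unaware of arm required? |
|---|---|---|
| Core lab (Protocol 5.1.2, 6.2.1; SAP 3.1.2) | Independent, blinded | Yes |
| Follow-up mRS/NIHSS assessor (Protocol 6.2.2) | Research team; independent physician preferred; not treatment team | No |
| Any clinical assessor (SAP 3.1.2) | Certified; not treatment team | No |
| Randomizer (Protocol 5.5) | Authorized research team member, or the neurointerventionalist | Knows the arm |
| Local coordinator (Protocol 8.1) | Enters study information, uploads source records | Can know the arm |

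No rule keeps the last two roles apart from the two assessor roles. The documents do not define the treatment team.

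**2. Which hypotheses are reached**

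Protocol 6.2.2 covers the 3-6 and 12-18 month visits, so it bears directly on H3, H4 and H5. H2 uses a 24-hour NIHSS, which Protocol 6.2.2 does not cover and the visit schedule in Protocol 6.1 does not list as a separate time point. For H2 only SAP 3.1.2 applies. Death (mRS 6, and death within 24 hours counted as morbidity under SAP 6.6.1) needs no rating, so the exposure is confined to survivors.

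**3. The plan's own figure**

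The plan gives no power figure for mRS or NIHSS. For the primary endpoint, SAP 6.5.2 gives 325 per arm, 73% versus 82%, two-sided 0.05 and about 80% power. With a pooled null variance:

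- Null SE = √(2 × 0.775 × 0.225 / 325) = 0.0328; critical difference = 1.96 × 0.0328 = 0.0642.
- Alternative SE = √((0.73 × 0.27 + 0.82 × 0.18) / 325) = 0.0326.
- Power = Φ((0.09 − 0.0642) / 0.0326) = 78.6%, consistent with the stated approximate figure. It is used in step 6.

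**4. Illustration for mRS**

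From the documents: 325 per arm, alpha 0.05. Assumed, because the documents give none: mRS 0-6 spread of 35/25/15/10/6/3/6% in both arms (no true effect), and a fraction *f* of larger-coil scores of 1-5 rated one category better. The test is a stand-alone, unstratified rank test, evaluated by simulation. SAP 6.6.3 plans van Elteren's test.

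Scores 1-5 make up 25 + 15 + 10 + 6 + 3 = 59% of patients, and survivors 94%. The share of survivors moved is therefore *f* × 59/94.

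| *f* | Survivors moved | Rejection rate |
|---|---|---|
| 0 | 0 | about 5% |
| 10% | about 6% | about 9% |
| 20% | about 13% | about 20% |
| 30% | about 19% | about 39% |

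Two other assumed spreads (45/25/10/8/4/2/6% and 30/25/15/12/6/4/8%) give about 9% at *f* = 10% and 20% at *f* = 20%. At *f* = 5% they stay near 6%.

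**5. Illustration for NIHSS morbidity**

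For a common true rate *p*, with scoring that adds *b* to one arm's observed rate, the rejection probability is Φ((b − c)/SE₁) + Φ((−b − c)/SE₁). Here c = 1.96 × the pooled SE. Example with *p* = 5%, *b* = 2 points: pooled SE = √(2 × 0.06 × 0.94 / 325) = 0.0186, c = 0.0365, SE₁ = 0.0186, giving about 19%.

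| Assumed true rate | +1 point | +2 points | +3 points |
|---|---|---|---|
| 3% | 11% | 26% | 45% |
| 5% | 9% | 19% | 34% |
| 10% | 7% | 13% | 22% |

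**6. Effect of the gatekeeping**

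Under SAP 6.8, H3 is formally tested only after H1 and then H2 reach p < 0.05. Assume H1 has its calculated power and the three tests are independent:

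- H2 unbiased at 5%: 0.786 × 0.05 × (0.09, 0.20, 0.39) = 0.4%, 0.8%, 1.5%.
- H2 biased, rejecting 19%: 0.786 × 0.19 × (0.09, 0.20, 0.39) = 1.3%, 3.0%, 5.8%.

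Independence is favourable to the plan: a bias shared by NIHSS and mRS would raise these figures.

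**The case against.** The plan has partial safeguards. Treating staff are excluded, an independent physician is preferred, the coordinator or nurse is only a fallback, and the SAP asks for certified staff. These reduce the exposure, but none of them is masking.

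A reader might infer that assessors will know the arm, or that one person will randomize, enter the coil log and score. The documents do not say so. They allow it by silence: Protocol 5.5 also lets the operator randomize, Protocol 5.1.2 does not name who completes the procedural form, and the coordinator's access follows only from the general wording of Protocol 8.1.

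A reader might also count four of the five hypotheses as separately compromised. There are two assessor-scored endpoints, since H4 and H5 are H3 by stratum, and H2 is reached only through the SAP.

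Finally, the 9/20/39% could be read as the trial's false-claim rate. It is the rate for one test taken alone. The hierarchy makes a formal false H3 claim much rarer (step 6). That objection stands for formal claims. It has less force for interpretation, because mRS results will be reported whether or not the hierarchy reaches them.

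**Conclusion.** The gap is real and limited in scope. Followed exactly, the plan permits unmasked scoring of 3-6 month mRS directly and of 24-hour NIHSS through SAP 3.1.2. Both are judgement-based scales in the formal hierarchy.

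Under the assumptions in step 4, shifting about 6/13/19% of larger-coil survivors by one mRS category lifts a stand-alone 5% test to about 9/20/39%. A smaller shift does little. The mRS spread, the shift sizes and the one-way direction are all assumed. The documents support no estimate of the actual bias or its sign, so the figures show sensitivity and do not predict anything.

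The point does not extend to the primary endpoint, which is read by a blinded core lab, or to deaths. It warrants a change to the plan, but does not threaten the trial's main conclusion.

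**What to change.** Amend Protocol 6.2.2 and SAP 3.1.2, naming the 24-hour NIHSS as well as the two follow-up visits:

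- State that the non-treating assessor already required should be masked to allocation.
- Where existing staff allow, that assessor should not be the person who randomized the patient or entered the procedure and coil data.
- Hide the arm and the coil log on the follow-up eCRF screens that assessors see.
- Record at each assessment whether the assessor knew the arm.
- Before data lock, pre-specify a sensitivity analysis of mRS and NIHSS by assessor awareness. The SAP's purpose statement allows revisions up to that point.

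**Cost.** This needs wording in two documents, an eCRF access setting, one extra field and one sensitivity analysis. Small sites may have to divide tasks among existing staff. Where a single coordinator does everything, hiding screens cannot mask that person. In that case the assessment is recorded as unmasked, and no new assessor is added. If some visits are already complete, masking can apply only to those remaining.
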